### 5.7.3 Premature Termination or Suspension of Study

This study may be temporarily suspended or prematurely terminated if there is sufficient reasonable cause. Written notification, documenting the reason for study suspension or termination, will be provided by the suspending or terminating party to all investigators, the funding agency, and regulatory authorities. If the study is prematurely terminated or suspended, the PI will promptly inform the IRB and will provide the reason(s) for the termination or suspension.

Circumstances that may warrant termination or suspension include, but are not limited to:

- Determination of unexpected, significant, or unacceptable risk to participants
- Demonstration of efficacy that would warrant stopping
- Insufficient compliance to protocol requirements
- Data that are not sufficiently complete and/or evaluable
- Determination of futility

Study may resume once concerns about safety, protocol compliance, data quality are addressed and satisfy the sponsor and/or IRB.

## 6 Behavioral/Social Intervention

### 6.1 Study Behavioral or Social Intervention(s) Description

The Aliviado DSD Caregiving Mastery Program is an mHealth based family caregiver intervention to promote prevention, detection, and management of DSD in the community. The DSD Caregiving Mastery program consists of training videos; symptom management algorithms; assessments; care plans; education articles; mobile push notification or text message reminders and encouragements; and brief communication guides to empower/activate caregivers to discuss probable DSD and deprescribing of delirium-inducing medications with their loved one's healthcare providers. The communication guides are provided to caregiver subjects when they obtain a positive result using the Family Confusion Assessment Method, or when a delirium-inducing medication is identified according to the 2023 updated Beers criteria in the medication list that they provided. Caregivers will be instructed to use these guides to speak with their loved one's health care provider. The training videos will cover the purpose of these guides, how to use these guides, the role of family caregiver in delirium prevention, and how to perform the Family Confusion Assessment Method. Their loved one's healthcare provider will be the one to confirm or rule out delirium based on his/her clinical assessment, as well as make recommendations about what to do with the specific delirium-inducing medication based on his/her clinical judgement (continue, stop, reduce dosage, etc.). See Attachment A for the existing delirium-related contents from the existing Alivaido Dementia Care program to be adapted for use by family caregivers. See Box 1 for topics of the training videos to be developed.

Table 2. Topics Covered in the DSD Training Videos for Family Caregivers

Existing Topics in the aide training video (will be shown to the family caregivers in Aim 1 codesign workshop as an example to elicit feedback on how to redesign the video for use by family caregivers)	New topics to be added to the family caregiver version of the training videos (informed by literature review)


• What is delirium?

• Symptoms of delirium

• Delirium vs dementia

• Delirium vs sundowning

• Common causes of delirium

 
Link to the existing aide training video.
	

▪ Important role families play in DSD care (

▪ Assess delirium using Family Confusion Assessment Method (FAM-CAM)

▪ 3 case vignettes to practice delirium assessment using FAM-CAM

▪ Daily prevention/management

▪ Prevention/management task while your loved one is hospitalized

▪ Discuss probable DSD/de-prescribing using the tailored communication guides

CONFIDENTIAL

This material is the property of the NYU Langone Health. Do not disclose or use except as authorized in writing by the study sponsor

Because the objective of the Aim 2 feasibility trial is to assess feasibility and acceptability of the intervention in family caregivers instead of efficacy or effectiveness of the intervention, there is no control intervention/treatment. No PLWD will be enrolled. No outcome data of PLWD will be collected. Information of PLWD will only be collected at baseline based on caregiver report in **anonymous** survey questionnaires (no personal identifiers of PLWD being collected).

### **6.1.1 Administration of Intervention**

Caregivers will first complete self-paced training videos (~60 minutes total) over a 2-week period, followed by a 4-week usability testing period in which caregivers will administer an app version of the Family Confusion Assessment Method weekly (~5 minutes/week), perform daily prevention or management tasks specified in a tailored, caregiver-developed care plan, and receive weekly push notification reminders and encouragements. In cases where push notifications are not feasible or cannot be delivered, SMS text messaging will serve as an alternative method to convey motivational messages. This approach ensures that the motivation messages related to the research study can still be reliably conveyed to participants. The DSD management algorithm identified in the literature will be simplified and presented as a series of questions to caregivers to guide tailoring of the care plan. Caregivers can choose to complete the training videos in the mHealth app or on the Aliviado website. Caregivers will learn how to administer the Family Confusion Assessment Method through watching the self-paced training videos.

All caregivers will receive a user manual that provides (1) instructions on how to complete the training/navigate the app; and (2) a log to record questions and daily tasks completed. If a delirium assessment is positive, a tailored communication guide will be provided to facilitate caregivers' discussion of probable DSD with a healthcare provider. If delirium-inducing medications are identified, a tailored communication guide will be generated to facilitate the discussion on de-prescribing.

At enrollment, caregiver's health literacy, caregiving self-efficacy, and comfort with technology will be assessed using the BRIEF Health Literacy Screening, the Revised Scale for Caregiving Self-Efficacy and the Functional Assessment of Comfort Employing Technology Scale to tailor additional support to caregivers (caregivers can decline this offer). For instance, weekly check-in calls will be offered to caregivers with low health literacy over the 2-week training period to ensure understanding of the training material using the teach back method. For caregivers with low self-efficacy, the PI will offer a 1:1 call at the end of the 2-week training period to help caregivers set incremental goals to carry out the care plan. At enrollment, caregivers will also complete the Modified Caregiver Strain Index. Those who score  $\geq 7$  will be offered referral to external support services such as NYU Alzheimer's Caregiving Program.

All caregivers can contact the NYU Meyers Aliviado Support Center for technical support; questions on how to perform assessments or specific care plan tasks will be forwarded to the PI. Caregivers' usage of the tailored additional support and the Support Center will be recorded and counted towards intervention dosage.

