Number of participants	Aim 1: 8 family caregivers Aim 2: 30 primary caregivers plus 0 to 30 optional secondary caregivers Optional: Enrolled primary caregivers can choose to invite additional relatives or friends to participate in the Aim 2 pilot study as "secondary caregivers".
Description of Study Intervention/Procedure	Intervention: Aliviado DSD Caregiving Mastery Program, a family caregiver intervention consisting of mHealth-app based educational videos and articles; caregiver-administered assessment tools and care plans; and motivational push notification or text message reminders and encouragements.
Reference Therapy	None
Key Procedures	None

CONFIDENTIAL

This material is the property of the NYU School of Medicine and Langone Health. Do not disclose or use except as authorized in writing by the study sponsor

Statistical Analysis	
Aim 1: Descriptive statistics to describe sample characteristics
 
Aim 2: Descriptive statistics will be calculated to summarize caregiver characteristics, feasibility, acceptability, and app usability outcomes. Paired t-tests will be performed to compare (1) changes in caregiver delirium knowledge and caregiving mastery from baseline to Week 2 (immediately post training), and (2) changes in delirium knowledge, caregiving mastery, strain, depression, and burden from baseline to posttest (Week 6).

----------------------	---

[figure not shown]
CONFIDENTIAL

This material is the property of the NYU Langone Health. Do not disclose or use except as authorized in writing by the study sponsor

Behavioral Intervention Template Version: 18 July 2022

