### **2.3.2 Risk of Use of Mobile Health Technology**

The study mHealth app will only be used to collect study data with IRB approval. Though breach of confidentiality or loss of privacy is possible, we anticipate that either is unlikely to happen because the mHealth app is NYU-housed with IT security approval for research sensitive data and is HIPAA compliant. Data will be collected directly from individual users from the app in an encrypted process where the app is run in a Heroku shield private dynos runtime environment and the data will be stored in a Postgres database housed within a Heroku shield private space encrypted and secured environment (same type of environment that runs the NYU Langone Health instance of the EPIC haiku app). The app does not access the user's camera or albums and does not track the user's physical activities. Any risks associated are outlined in the informed consent, as follows:

"The optional testing of the beta version of the mHealth app may also subject you to potential risks of breach of confidentiality and psychological distress. However, we anticipate that the likelihood of these potential

CONFIDENTIAL

This material is the property of the NYU Langone Health. Do not disclose or use except as authorized in writing by the study sponsor

risks should be similar to participating in the main co-design workshop and should not exceed what you would expect from your normal day-to-day use of apps that you download from an app store." (Aim 1)

"The Aliviado mHealth app is HIPAA compliant. The use of the Aliviado mHealth app to collect study data is approved by the NYU Grossman School of Medicine. Any information that you enter the Aliviado mHealth app is considered research data. Your data will be de-identified and aggregated with data from other study participants before we perform data analysis. Your data will be processed in an encrypted process and stored within an encrypted and secured environment. Potential risks associated with the use of the study mHealth app include loss of privacy and breach of confidentiality; however, these potential risks would not exceed what you would expect from your normal day-to-day use of commercially available mobile health technology such as apps that you download from an App store." (Aim 2)

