## 4.2 Study Endpoints

### 4.2.1 Primary Study Endpoints

Aim 1 co-design workshop: NA (The purpose of the co-design workshop is to understand caregiver participants' preferences of the intervention contents and app features; no intervention is implemented at this stage and no outcome data collected.)

Aim 2 feasibility trial: Because this is a pilot feasibility study instead of an efficacy or effectiveness trial, the primary study endpoints are feasibility, acceptability, and app usability:

- Feasibility is indicated by (1) successful enrollment of 30 primary caregivers and (2) 85% retention.
- Acceptability is indicated by: (1) >80% of primary caregiver participants reporting high program satisfaction and willingness to recommend this program to others; (2) >80% of primary caregiver participants completing all training videos within the target 2-week timeframe (Week 1-Week 2); and (3) >80% primary caregiver participants successfully complete the weekly delirium screening at least twice over the 4-week implementation period (Week 3-Week 6).
- App usability is assessed by a modified IBM Computer Usability Satisfaction Questionnaire at Week 6 (final visit).

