Aim 2 feasibility trial: n=30 to 60 (30 primary caregivers + 0-30 optional secondary caregivers); single site. The enrollment goal is 30 primary caregiver participants. The 30 enrolled primary caregivers are allowed to invite additional family members or friends to participate in the study and enroll as secondary caregivers. However, the enrollment of secondary caregivers is optional, and thus, we anticipate 0 to 30 secondary caregivers will be enrolled. To ensure the study is adequately powered, we need 26 evaluable primary caregiver participants who complete the study. We will recruit additional primary caregivers if more than 4 primary caregivers drop out of the study, or the number of primary caregiver participants who complete the study has not reached 26. Single site: All participants will be screened, enrolled, and consented at the NYU Site; all data will be collected and stored in the password-protected NYU REDCap or NYU Box as appropriate. Data will be deidentified before uploading to NYU Box. Subjects will be recruited from a list of potentially eligible caregivers identified in the data pull performed by the DataCore. The screening and consenting of all caregiver subjects will be completed by the PI or an NYU research assistant trained by the PI following the “Remote e-Consenting” process using “REDCap” as described in the [“Use of Electronic Informed Consent”](#) guidance document. We will create the REDCap version of the IRB-approved consent form following the [NYU Health Science Library video series on eConsent](#).

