### **6.1.2 Procedures for Training Interventionalists and Monitoring Intervention Fidelity**

The PI and the Aliviado Support Center will facilitate caregiver subjects' accessing the intervention. Intervention fidelity will be assessed through automatically tracking caregivers' completion of the self-paced training videos and Family Confusion Assessment Methods in the mHealth app. Fidelity of implementation of daily DSD prevention/management tasks will be assessed through reviewing caregivers' task completion log (available in the user manual provided to the caregiver).

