**Week 2 Visit (Immediately Post Training): n=30 primary caregivers + up to 30 secondary caregivers**

- Collect data on caregiver participants’ delirium knowledge and DSD caregiving mastery in an online REDCap survey questionnaire.

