#### 14.1.2 Data Collection Tools – Mobile Health Technology

##### Products and Devices

The Aliviado mHealth app is NYU-housed and will only be used to collect study data with IRB approval and if the subject has agreed to all applicable Terms of Service. The Aliviaod mHealth app does not include location tracking services. The app will not track participants' geographic location or physical activities. Time logged in to the app, number of care plans and assessments completed, number of videos watched, etc. will be automatically tracked by the Aliviado app (app usage).

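### Would training videos watched on the Aliviado website be missed when the video-completion criterion is counted?

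*Combined protocol and SAP*

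**What the plan says.** Section 6.1.1 leaves the route for the training videos to the caregiver: "Caregivers can choose to complete the training videos in the mHealth app or on the Aliviado website". The Protocol Summary is narrower and describes "a family caregiver intervention consisting of mHealth-app based educational videos and articles".

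Two places deal with tracking. Section 14.1.2, which is about the app, lists among the items recorded the "number of videos watched, etc. will be automatically tracked by the Aliviado app (app usage"). Section 6.1.2 says that fidelity will be assessed by automatic tracking of "completion of the self-paced training videos and Family Confusion Assessment Methods in the mHealth app".

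Video completion is used three times. Acceptability criterion (2) in section 4.2.1 asks for ">80% of primary caregiver participants completing all training videos within the target 2-week timeframe (Week 1-Week 2"). Section 10.4.5 uses the count of videos watched as an adherence measure. The same section enters the degree of video completion in an exploratory linear mixed model for knowledge gains. Under section 10.4.2 the primary endpoints are summarised descriptively with 95% confidence intervals.

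**The concern.** The website option appears in section 6.1.1 and is not carried through. The summary speaks of app-based videos, and section 14.1.2 describes a record kept by the app. The data listed for the Week 2 visit in section 7.1.1 are "delirium knowledge and DSD caregiving mastery in an online REDCap survey questionnaire", and neither Table 4 nor the schedule of events in Attachment C has an item for video completion. A reader could conclude that a caregiver who watches everything on the website leaves no trace.

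If so, the recorded completion rate would be too low, and the benchmark in a primary endpoint could be missed although the training was well accepted. The adherence count and the dose model would carry the same error. With about 30 caregivers, a handful of lost completions is enough to matter. Section 10.1 says that no separate analysis plan will be written, so no later document of that kind is expected to settle the point.

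**Working it through.** The documents give no figure to reproduce on this point. The check is a comparison of the passages, followed by the threshold arithmetic that shows what could be at stake.

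**1. Does any section say that website viewing is untracked?** No. Section 14.1.2 is confined to the app, so it naturally describes app usage only; its silence on the website is not a statement about the website. In section 6.1.2 the closing phrase about the app may attach to both items or only to the Family Confusion Assessment Method. On the second reading, completion of the videos is tracked automatically whatever the route.

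**2. Does any section restrict which completions count?** No. Section 6.1.1 says that videos can be completed by either route, and criterion (2) asks whether they were completed. The adherence and dose measures in section 10.4.5 are equally neutral. The summary is a short description of the programme and does not withdraw the option given in section 6.1.1.

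**3. Does the absence of a video item in the visit data show a gap?** No. Those lists cover questionnaires. Viewing in the app is absent from them too, although it is certainly recorded.

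**4. Is individual progress likely to be known?** Section 7.3.3 times the second one-to-one visit immediately after each participant has finished the videos (Week 2, +/-5 days), which the team can do only if it knows who has finished. The sample messages in Attachment D refer to a Learning Center, to progress by video and to a completion certificate. This is indirect evidence, but it points one way.

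**5. Thresholds.** The smallest count above 80% of n is k = floor(0.8 × n) + 1. Section 5.6 gives 30 enrolled primary caregivers. It also says that "we need 26 evaluable primary caregiver participants who complete the study"; that is the number needed for power and not a stated denominator for this criterion, so it is shown only as a variant.

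| n | k | k/n | Margin n − k | Rate if six of n completions are lost (exact 95% CI) |
|---|---|---|---|---|
| 30 | 24 + 1 = 25 | 83.3% | 5 | 24/30 = 80.0% (61% to 92%) |
| 26 | 20 + 1 = 21 | 80.8% | 5 | 20/26 = 76.9% (56% to 91%) |

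So even with full true completion, a sixth uncounted caregiver misses the benchmark. The intervals are Clopper-Pearson.

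**6. Conditional worst case.** Assume true completion of 95%, a share w of caregivers using the website, and every website completion lost. The recorded count is then binomial with n = 30 and p = 0.95 × (1 − w), and the chance of meeting the benchmark is P(X ≥ 25).

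| w | p | P(X ≥ 25) |
|---|---|---|
| 0% | 0.950 | 99.7% |
| 10% | 0.855 | 73.8% |
| 20% | 0.760 | 24.0% |
| 30% | 0.665 | 3.4% |

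The 95% and the values of w are assumptions; the documents give neither. The table also needs every website view to be lost, which steps 1 to 4 do not support. If website views are captured, the first row applies whatever w is.

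**The case for a change.** The best case for a change is that criterion (2) has a two-week window, so it needs a dated record for each caregiver. The protocol names one only for the app. A certificate that the caregiver is asked to keep is not a named data source, and the log in the user manual covers questions and daily tasks, not videos. With no separate analysis plan, the protocol is the natural place for such a statement, and one sentence would do.

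Part of this stands: no section names the record to be used for website completion. But naming a source log is operational detail of the kind that belongs in a manual of procedures. Section 14.3 refers to such a manual, and it is not before us. The sentence would confirm what the text already means and would alter no estimate, denominator or test.

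Going further would not help. A rule that a caregiver without a record counts as not completed is a separate choice about missing data; if website logging were incomplete, that rule would itself produce the undercount that is feared.

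**Conclusion.** The concern does not call for a change. The wording is uneven: section 6.1.1 allows two routes, the summary mentions one, and the only unambiguous tracking text is about the app. On a plain reading, completion by either route already counts towards criterion (2), the adherence count and the dose model, and an analyst would gather both records and count them together.

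The effect is zero if website views are recorded. It could reach a missed benchmark only if at least six completions out of 30 were lost, and nothing in the documents says that any would be. Even then, the result is a descriptive proportion with a wide interval, and no section ties it to a decision to proceed or stop.

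This conclusion rests on two assumptions: that the website or the Week 2 contact yields a dated record for each caregiver, which section 7.3.3 and Attachment D suggest but do not state, and that the denominator is the enrolled primary caregivers. A sentence naming the website record would be an editorial courtesy, not a correction.

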### **6.1.2 Procedures for Training Interventionalists and Monitoring Intervention Fidelity**

The PI and the Aliviado Support Center will facilitate caregiver subjects' accessing the intervention. Intervention fidelity will be assessed through automatically tracking caregivers' completion of the self-paced training videos and Family Confusion Assessment Methods in the mHealth app. Fidelity of implementation of daily DSD prevention/management tasks will be assessed through reviewing caregivers' task completion log (available in the user manual provided to the caregiver).

### **6.1.3 Assessment of Subject Compliance with Study Intervention**

Caregivers' compliance with study intervention will be assessed through reviewing caregivers' daily task completion log during the 3rd and final data collection session.

CONFIDENTIAL

This material is the property of the NYU Langone Health. Do not disclose or use except as authorized in writing by the study sponsor

